11.5 ELECTRONIC DIARY CARD

Subjects will be required to record the following information each day in a subject e-diary during study participation:

- Confirmation of administration of daily (every 24 hours) dose of RA101495 that includes date, time, and location of injection of RA101495

Subject e-diaries will be collected/dispensed at the time points shown in the Time and Events Table (Table 1). Subjects will be given detailed instructions on how to complete entries in subject diaries throughout study participation.

11.6 EXPLORATORY ASSESSMENTS

11.6.1 QUALITY OF LIFE ASSESSMENTS

Quality of life assessments will be performed according to the Time and Events Table (Table 1). The following QOL questionnaires will be used during this study:

- European Organization for the Research and Treatment of Cancer Quality of Life Questionnaire-C30 (EORTC-QLQ-C30)
- Functional Assessment of Chronic Illness Therapy-Fatigue (FACIT-Fatigue) Scale
- EuroQol-5D (EQ-5D)

11.6.1.1 EORTC-QLQ-C30

The EORTC QLQ-C30 consists of 30 questions, which are incorporated into 5 functional domains (physical, role, cognitive, emotional, and social domains); a global health status/global QOL scale; 3 symptom scales (fatigue, pain, and nausea and vomiting scales); 6 single items that assess additional symptoms (e.g. dyspnea, appetite loss, sleep disturbance, constipation, and diarrhea); and the perceived financial burden of illness treatment [Aaronson, 1993; Aaronson, 1996]. Subjects answer questions based on symptoms/status over the preceding week.

11.6.1.2 FACIT-FATIGUE

The FACIT-Fatigue Scale is a 13-item, easy to administer tool that measures an individual's level of fatigue during their usual daily activities over the preceding week. The level of fatigue is measured on a five point ordinal scale (4 = not at all fatigued to 0 = very much fatigued) [Webster, 2003].

11.6.1.3 EQ-5D

The EQ-5D is a standardized instrument for measuring generic health status. The EQ-5D consists of the EQ-5D descriptive system and the EQ visual analogue scale (VAS). The EQ-5D descriptive system comprises the following 5 dimensions: mobility, self-care, usual activities, pain/discomfort and anxiety/depression; each dimension has 3 levels: no problems, some problems, extreme problems [EuroQol, 1990]. Subjects answer questions based on symptoms and health status on the day the questionnaire is completed.

11.6.2 TREATMENT SATISFACTION QUESTIONNAIRE

A treatment satisfaction questionnaire using a 5-point Likert response scale will be administered to all subjects to assess overall satisfaction with SC administration of the study medication at the end of the 12-week Treatment Period.

A more targeted questionnaire using a 5-point Likert response scale will be administered to the Cohort B (Switch) subjects only to assess their preference for daily SC self-injection at home compared with biweekly infusions given by a health-care professional in the clinic.

11.6.3 BIOMARKERS

Blood samples will be collected at designated time points, concomitant with PK and PD sampling (see Table 1). All biomarkers will be analyzed by biological or biochemical assays at an accredited laboratory. Detailed instructions regarding sample collection, processing, and shipping will be provided in a separate laboratory manual.

The study of biomarkers related to complement function, thrombosis, inflammation, and liver function will provide further insight in to the clinical efficacy and safety of RA101495 in PNH subjects. Complement protein levels and complement activity will be tested to evaluate response to RA101495 and understand subject characteristics related to variations in response to drug. Markers of thrombosis and inflammation will be tested to assess correlation with complement function and clinical response to RA101495 and to identify markers that may correlate with thrombotic risk in PNH subjects. Additionally, markers for liver function will be assessed to evaluate tolerability of RA101495. A list of analytes will be created through review of the literature, ongoing clinical studies, and ongoing exploratory work and may be finalized after completion of the study.

The completion of these investigations may be conditional based on the results of this or other clinical studies, and samples may be selected for analysis on the basis of clinical outcome. The results of the biomarker investigations may be reported separately from the main clinical study report.

11.6.4 PHARMACOGENOMIC ASSESSMENTS

Participation in the pharmacogenomic assessment is optional and subjects must consent to the pharmacogenomic analysis using a separate consent form.

For subjects who opt to participate in pharmacogenomics studies, a blood sample will be obtained on Day 1. All genomic analyses will be performed at an accredited laboratory. Detailed instructions regarding sample collection, processing, and shipping will be provided in a separate laboratory manual.

Genomic studies will be performed (e.g. deoxyribonucleic acid [DNA] sequencing, DNA copy number analysis, ribonucleic acid [RNA] expression profiling) to explore whether specific genomic features correlate with response or resistance to study drug.

The completion of these investigations may be conditional based on the results of this or other clinical studies, and samples may be selected for analysis on the basis of clinical outcome. The results of the genomic investigations may be reported separately from the main clinical study report.

12 SAFETY REPORTING

12.1 DEFINITIONS

12.1.1 ADVERSE EVENT

An AE is any untoward medical occurrence in a subject administered a pharmaceutical product and which does not necessarily have a causal relationship with this treatment. An AE can therefore be any unfavorable and unintended sign (including a clinically significant abnormal laboratory finding, for example), symptom, or disease temporally associated with the use of a medicinal product, whether or not considered related to the medicinal product.

The following are not considered to be AEs despite requiring hospitalization:

- Pre-existing conditions that, in the opinion of the investigator, did not worsen or progress during study participation
- Routinely scheduled procedures or treatment
- Elective procedures that had been scheduled prior to study participation (i.e. signing of the ICF)

12.1.2 SERIOUS ADVERSE EVENT

An SAE is any untoward medical occurrence that:

- results in death
- is life-threatening (note that this refers to an event in which the subject was at risk of death at the time of the event; it does not refer to an event that hypothetically might have caused death if it were more severe)
- requires hospitalization or prolongation of existing hospitalization
- results in persistent or significant disability/incapacity
- results in a congenital anomaly/birth defect

An SAE may also be any other important medical event that may not be immediately life-threatening or result in death or hospitalization, but may jeopardize the subject or require intervention to prevent one of the other outcomes listed in the definition above. Examples of such events include intensive treatment in an emergency room or at home for bronchospasm, hyperkalemia, or convulsions that do not result in a formal hospitalization.

Elective hospitalizations scheduled prior to study participation (i.e. signing of the ICF) should not be reported as SAEs.

12.1.3 ADVERSE EVENTS OF SPECIAL INTEREST

12.1.3.1 THROMBOTIC ADVERSE EVENTS

All subjects should be monitored for signs and symptoms of thrombotic events at all study visits (weekly for the first 4 weeks followed by every 2 weeks). The method of diagnosis (e.g. ultrasound, computed tomography [CT], magnetic resonance imaging [MRI], venogram, or other [specify]) for any reported event should be recorded in the eCRF. All AEs should be recorded as AEs per Section 12.1 and Section 12.3.

12.1.3.2 HEPATIC ADVERSE EVENTS

All subjects should be monitored for signs and symptoms of hepatic or biliary dysfunction. Liver function tests (LFTs) (ALP, ALT, AST, GGT, Direct Bilirubin and Indirect Bilirubin) are monitored weekly for the first 4 weeks followed by every 2 weeks during the study. The following guideline is provided:

- In subjects with isolated ALT elevation $>2xULN$ or direct bilirubin and ALP elevation $>2xULN$ with no other explanation for the elevation(s), contact the medical monitor to review the case details and determine if the subject should continue or discontinue study treatment. The subject should be monitored until the elevated enzymes return to Grade 1 (NCI CTACE) or lower.
- Subjects with isolated ALT elevations $>3xULN$ concurrently with bilirubin elevation $\geq 2xULN$ and a normal ALP with no other explanation for the elevation should be permanently discontinued. The medical monitor should be contacted as soon as possible to review the case. The subject should be monitored until the elevated enzymes return to Grade 1 (NCI CTACE) or lower.

All AEs should be recorded as AEs per Section 12.1 and 12.3.

12.1.3.3 PANCREATIC ENZYME ELEVATIONS

Subjects should be monitored during the study for symptoms of pancreatitis or cholecystitis. Pancreatic enzymes (amylase and lipase) are monitored weekly for the first 4 weeks followed by every 2 weeks during the study.

In subjects with elevations of amylase or lipase to National Cancer Institute Common terminology Criteria for Adverse Events (NCI CTCAE) Grade 3 ($>2.5xULN$) or Grade 4 ($>5xULN$) contact the medical monitor to review the case details and determine if the subject should continue on study treatment. The subject should be monitored until amylase and/or lipase returns to Grade 1 or lower.

All AEs should be recorded as AEs per Section 12.1 and Section 12.3

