	
events (AEs).
 
The risk of Neisseria meningitidis infection will be closely monitored during the study. During the screening period, prior to study entry, all subjects must have a documented negative result for Neisseria meningitidis colonization via a throat swab. All Cohort A (Naïve) subjects who have not been previously vaccinated against Neisseria meningitidis prior to study entry must be vaccinated and must receive ciprofloxacin for 14 days starting with the first dose of RA101495 at the Day 1 Visit. A booster vaccination should also be administered as clinically indicated according to the local standard of care. All Cohort B (Switch) subjects must have documentation of prior Neisseria meningitidis vaccination (and booster if appropriate) prior to study entry.
 
For Cohort A (Naïve) subjects, the Day 1 Visit may be scheduled at any time after Screening and confirmation of eligibility. For Cohort B (Switch) subjects, the Day 1 Visit should be scheduled to coincide with the next scheduled dose of eculizumab (i.e. 14 ± 2 days after from the last eculizumab dose). Eculizumab should NOT be administered at the Day 1 Visit or at anytime thereafter during the study
 
During the Treatment Period, to mitigate the risk of infection, subjects will be counseled and reminded of early signs and symptoms of Neisseria meningitidis infection. A patient safety card detailing the signs and symptoms of infection with instructions to seek immediate medical attention will be provided to each subject. The card will also describe the subject’s participation in the study and the risks of infection associated with inhibition of the terminal complement system. The patient safety card must be carried with the patient at all times while on treatment.
 
At the conclusion of the Treatment Period subjects who complete the study and are demonstrating benefit will have the option to enroll in an extension study to continue receiving treatment with RA101495. Alternatively, they may opt to receive standard-of-care treatment off study, after consultation with their treating physician. If the subject withdraws early from the RA101495-01.201 study for any reason, he/she will not be eligible for the extension study.
 
All subjects will receive a loading dose of 0.3 mg/kg to be administered subcutaneously (SC) at the Day 1 visit. Following in-clinic education and training, all subjects will self-administer daily SC doses of 0.1 mg/kg of RA101495 for 12 weeks. Except for Day 1, on study clinic days, the dose should be administered after the PK and PD collection has been completed.
 
From the Week 2 Visit onwards, if a subject has not achieved an adequate response (defined as a lactate dehydrogenase [LDH] <1.5 x ULN), and following evaluation of safety and tolerability data by the investigator and the medical monitor, the dose should be escalated to 0.3 mg/kg daily. The dose may also be escalated to 0.3 mg/kg daily at any time in the event of an overt breakthrough hemolysis episode (e.g. hemoglobinuria).

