- b. For Cohort A (Naïve) subjects, the Day 1 Visit may be scheduled at any time after Screening and confirmation of eligibility. For Cohort B (Switch) subjects, the Day 1 Visit should be scheduled to coincide with the next scheduled dose of eculizumab (i.e. 14 ± 2 after from the last eculizumab dose). Eculizumab should NOT be administered at the Day 1 Visit or at any time thereafter during the study.
- c. Height will be measured only at the Screening Visit.
- d. All subjects must have a negative throat swab for *Neisseria meningitidis* infection for eligibility. All subjects in Cohort A must be vaccinated against *Neisseria meningitidis* and should have a booster as indicated by standard of care. All subjects in Cohort A must receive ciprofloxacin to be taken orally on Days 1 to 14. All Cohort B subjects must have documentation of prior *Neisseria meningitidis* vaccination (and booster if appropriate) prior to study entry.
- e. Including LDH for primary efficacy endpoint
- f. Coagulation tests should be performed, according to standard practice, on all subjects taking anticoagulant therapy.
- g. For all female subjects of childbearing potential, a negative serum pregnancy test must be documented at the Screening Visit and a negative urine pregnancy test must be documented at the Day 1 Visit prior to dosing. All other pregnancy tests will be urine.
- h. The injection site should be assessed at each clinic visit through Day 84 (End of Study).
- i. Blood samples for PK and PD and additional biomarker sampling at the following time points in relationship to the first dose of RA101495: pre-dose (within 1 hour before first dose administration) and at 1, 3, and 6 hours post-dose on Day 1. For subjects who have a dose increase to 0.3 mg/kg, samples for PK and PD should be collected at pre-dose Day 1 of the new dose, see footnote j. On clinic visit days, PK and PD samples should be collected prior to administration of RA101495.
- j. For subjects in Cohort B only, blood samples for PK of eculizumab should be collected at screening, Day 1, Day 15, Day 29, and Day 43. (at 2-week, 4-week, and 6-week) Visits. The sample should be collected prior to administration of RA101495.
- k. Blood sample for ADA on Day 1 must be obtained prior to dosing of RA101495.
- l. Blood sample for optional pharmacogenomic testing must be obtained on Day 1.
- m. On clinic visit days, the study drug RA101495 should be administered after blood samples for PK and PD are collected.

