12.2 EVALUATION AND CLASSIFICATIONS

12.2.1 SEVERITY

The investigator should determine the severity of the reported AE by using the NCI-CTCAE (Version 4.0). These criteria will be provided in a separate manual.

For any reported AE not described in the NCI-CTCAE, the following guidelines must be considered for severity evaluation:

Adverse Event Severity

Mild	Symptom(s) barely noticeable to subject or does not make subject uncomfortable; does not influence performance or functioning; prescription drug not ordinarily needed for relief of symptom(s).
Moderate	Symptom(s) of a sufficient severity to make subject uncomfortable; performance of daily activity is influenced; subject is able to continue in study; treatment for symptom(s) may be needed.
Severe	Symptom(s) cause severe discomfort; symptoms cause incapacitation or significant impact on subject's daily life; severity may cause cessation of treatment with study treatment; treatment for symptom(s) may be given and/or subject hospitalized.

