13.3.4.2.3 PANCREATIC ENZYME ELEVATIONS

Pancreatic AEs and will be summarized separately by system organ class, preferred term, and cohort. Pancreatic elevations will be summarized by changes from baseline and graded in severity using the NCI CTCAE criteria.

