3.8.3.2 Pancreatic Enzymes: NCI CTCAE Grading

Amylase and lipase values will be summarized via the NCI CTCAE criteria provided in Table 8.

Table 8: CTCAE Grading Criteria for Selected Pancreatic Enzyme Tests

Lab Test	Grade/Criteria					Grade/Criteria			
	1	2	3	4					
amylase	> 1.0 – 1.5	>1.5 – 2.0	>2.0 - 5.0	> 5.0					
	(x ULN)	(x ULN)	(x ULN)	(x ULN)					
limana	> 1.0 – 1.5	>1.5 – 2.0	>2.0 - 5.0	> 5.0					
lipase	(x ULN)	(x ULN)	(x ULN)	(x ULN)					
Grading criteria based on Common Terminology Criteria for Adverse Events (CTCAE) v4.03									

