14.2.14.6	Summary of FACIT-Fatigue: Items Shift Table; Per Protocol
	Population
14.2.15.1	Summary of EQ-5D: Health State VAS Score; Safety
	Population
14.2.15.2	Summary of EQ-5D: Health State VAS Score; Per Protocol
	Population

Table Number	Table Title
14.2.15.3	Summary of EQ-5D: Individual Dimensions; Safety
	Population
14.2.15.4	Summary of EQ-5D: Individual Dimensions; Per Protocol
	Population
14.2.15.5	Summary of EQ-5D: Individual Dimensions Shift Table;
14.2.13.3	Safety Population
14.2.15.6	Summary of EQ-5D: Individual Dimensions Shift Table; Per
	Protocol Population
14.2.16.1	Summary of Treatment Satisfaction; Safety Population
14.2.16.2	Summary of Treatment Satisfaction; Per Protocol Population
14.3.1.1	Overall summary of Treatment Emergent Adverse Events;
14.3.1.1	Safety Population
14.3.1.2.1	Incidence of Treatment Emergent Adverse Events by System
14.3.1.2.1	Organ Class and Preferred Term; Safety Population
	Incidence of Treatment Emergent Adverse Events by System
14.3.1.2.2	Organ Class, Preferred Term, and Maximum Severity; Safety
	Population
	Incidence of Treatment Emergent Adverse Events by System
14.3.1.2.3	Organ Class, Preferred Term, and Relationship to Study Drug;
	Safety Population
	Incidence of Treatment Emergent Adverse Events Leading to
14.3.1.2.4	Discontinuation of Study Drug by System Organ Class and
	Preferred Term; Safety Population
14.3.1.3	Listing of Serious Adverse Events by System Organ Class and
11.3.1.3	Preferred Term; Safety Population
	Incidence of Thrombotic Treatment Emergent Adverse Events
14.3.1.4	by System Organ Class, and Preferred Term; Safety
	Population
14.3.1.5	Summary of Injection Site Reaction Assessments; Safety
	Population
14.3.2.1	Summary of Hematology Values; Safety Population
14.3.2.2	Summary of Clinical Chemistry Values; Safety Population
14.3.2.3	Summary of Coagulation Values; Safety Population
14.3.2.4	Summary of C-Reactive Protein and Creatine Phosphokinase
1	Values; Safety Population
14.3.2.5	Summary of Liver Function Test Values – NCI CTCAE
11.5.2.5	Grading; Safety Population
14.3.2.6	Summary of Pancreatic Enzyme Test Values – NCI CTCAE
	Grading; Safety Population
14.3.2.7	Summary of Urinalysis Values; Safety Population
14.3.3	Summary of PNH Clone Size Values
	Safety Population

Table Number	Table Title
14.3.4	Summary of Vital Signs; Safety Population
14.3.5.1	Summary of ECG Interpretation; Safety Population
14.3.5.2	Summary of ECG Values; Safety Population

Figure Number	Figure Title

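### Protocol 12.1.3.3 prints CTCAE Grade 3 amylase or lipase as >2.5xULN, while SAP Table 8 starts Grade 3 at >2.0xULN, so a result tabulated as Grade 3 can fall below the printed trigger for medical-monitor review

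*Protocol*

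**What the plan says.** Protocol 12.1.3.3 covers pancreatic enzyme elevations as events of special interest. For amylase or lipase at NCI CTCAE "Grade 3 ($>2.5xULN$) or Grade 4 ($>5xULN$) contact the medical monitor to review the case details", with the purpose of deciding whether the subject stays on study treatment. It then adds a follow-up rule: "The subject should be monitored until amylase and/or lipase returns to Grade 1 or lower".

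The protocol relies on CTCAE grades elsewhere too. Section 12.2.1 has investigators grade reported adverse events by version 4.0, supplied as a separate manual. Section 13.3.4.2.3 says of the analysis: "Pancreatic elevations will be summarized by changes from baseline and graded in severity using the NCI CTCAE criteria".

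SAP 3.8.3.2 carries this out: "Amylase and lipase values will be summarized via the NCI CTCAE criteria provided in Table 8". Table 8 cites v4.03 and gives the same bands for both enzymes:

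- Grade 1: >1.0 to 1.5xULN
- Grade 2: >1.5 to 2.0xULN
- Grade 3: >2.0 to 5.0xULN
- Grade 4: >5.0xULN

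The result is reported in SAP Table 14.3.2.6.

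**The concern.** One grade name carries two different lower bounds. The protocol does not offer 2.5xULN as a free-standing alert level; it prints the number as the meaning of CTCAE Grade 3. A site that reads the grade name and looks it up, and a site that reads the multiple in parentheses, could therefore act differently on the same laboratory result.

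The contact with the medical monitor is the only enzyme-specific decision step in 12.1.3.3. If it is not triggered, the stated question of whether the subject should continue dosing is not put at that point. The study report could then show Grade 3 amylase or lipase values for which the printed rule asked for no review. The trigger should be unambiguous here: according to Protocol 6.3, earlier repeat dosing in humans was four subjects at 0.2 mg/kg for 7 days, whereas this study doses for 12 weeks and allows escalation to 0.3 mg/kg daily.

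**Working it through.** No power, error-rate or sample-size figure is involved. The check compares thresholds, with x the result as a multiple of ULN.

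**Inputs**

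| Item | Source | Value |
|---|---|---|
| Printed Grade 3 trigger | Protocol 12.1.3.3 | x > 2.5 |
| Printed Grade 4 trigger | Protocol 12.1.3.3 | x > 5 |
| Grade 3 for tabulation | SAP Table 8 | 2.0 < x ≤ 5.0 |
| Grade 4 for tabulation | SAP Table 8 | x > 5.0 |
| Grade 1 for tabulation | SAP Table 8 | 1.0 < x ≤ 1.5 |
| Entry limit, amylase or lipase | Protocol 9.2, criterion 4 | excluded if x > 2 |

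**Step 1. Grade 4.** Both documents use 5xULN. They agree.

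**Step 2. Lower bound of Grade 3.** 2.5 − 2.0 = 0.5xULN, for amylase and for lipase.

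**Step 3. Results treated differently.** The SAP assigns Grade 3 or higher when x > 2.0. The printed multiple triggers contact when x > 2.5. They disagree when x > 2.0 and x ≤ 2.5. Spot values:

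| x | SAP grade | Printed trigger met? |
|---|---|---|
| 2.0 | 2 | no |
| 2.01 | 3 | no |
| 2.3 | 3 | no |
| 2.5 | 3 | no |
| 2.51 | 3 | yes |
| 5.1 | 4 | yes |

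At or below 2.0, and above 2.5, the two rules agree on whether a result is Grade 3 or higher.

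**Step 4. Width of the band.** SAP Grade 3 spans 5.0 − 2.0 = 3.0xULN. The band covers 0.5 / 3.0, about 17% of that range. This is a share of the scale, not of patients or results. The documents give no distribution of either enzyme, so no count can be computed.

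**Step 5. Follow-up rule.** Under Table 8, a return to Grade 1 or lower means x ≤ 1.5. That rule sits in the same paragraph as the trigger. Amylase and lipase are nevertheless in the chemistry panel (Protocol Table 4), which is drawn at every visit whatever the last result (Protocol Table 1).

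**Step 6. Comparison with entry.** Exclusion criterion 4 uses 2xULN, the same value as the lower bound of Grade 3 in Table 8. A result in the band would bar a subject from entry but would not meet the printed on-treatment multiple.

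**Step 7. After the fix.** With the printed trigger set to x > 2.0, no value satisfies x > 2.0 and x ≤ 2.0. The band is empty: every result the SAP tabulates as Grade 3 or 4 also triggers contact.

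**The case against.** The strongest reply is that little is lost in practice. The trigger names the grade before the number, and investigators hold the CTCAE manual under 12.2.1. A site that grades from the manual would call at the manual's Grade 3. This stands: only a site using the printed multiple, with a result above 2.0 and up to 2.5xULN, would miss the contact.

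A reader might infer that subjects in the band would go without enzyme monitoring. The documents do not support that. Both enzymes are measured weekly for four weeks and then every two weeks regardless of the value. Clinically significant laboratory values are captured as adverse events (12.3.1.1), and all adverse events are followed until they resolve or stabilise (12.3.2). The sponsor also reviews safety data as they accrue (13.3.7). The follow-up that could still be lost is narrow: enzyme checks after the last visit for a value never recorded as an adverse event. None of these safeguards specifies the monitor contact at this threshold.

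A second reply is that 2.5xULN may be intended. The CTCAE text is not part of the documents, the protocol cites version 4.0 and the SAP v4.03, and Table 8 governs tabulation rather than site conduct. The protocol does set its own alert levels elsewhere: in 12.1.3.2, monitor contact for isolated ALT elevation begins at 2xULN, which is not a grade boundary in any row of SAP Table 7. That is a fair point about the number. It does not rescue the label, because the ALT rule states its multiple without a grade, whereas 12.1.3.3 calls 2.5xULN Grade 3.

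**Conclusion.** The mismatch is real and narrow. The protocol's review trigger and the SAP's grading table give the same CTCAE grade two lower bounds, 0.5xULN apart, for amylase and for lipase. What can be missed is the specified discussion of whether to continue treatment, for a result above 2.0 and up to 2.5xULN at a site that follows the printed multiple. The number of such results is unknown and may be zero in a study of at most 20 subjects. Nothing in the LDH endpoint, the sample size or the efficacy analysis depends on it.

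That 2.0xULN is the correct Grade 3 bound rests on SAP Table 8 and its citation of v4.03. The inconsistency itself does not depend on which number is right.

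A reader might also treat the ciprofloxacin wording as a second contradiction that adds weight here. It does not. Footnote d of the Time and Events table says "All subjects in Cohort A must receive ciprofloxacin to be taken orally on Days 1 to 14". The synopsis says that Cohort A subjects not vaccinated "prior to study entry must be vaccinated and must receive ciprofloxacin for 14 days starting with the first dose of RA101495"; sections 8.1, 11.2.5.1 and 12.1.3.5 likewise require the course for the unvaccinated. None of them confines it to those subjects, so a site following footnote d breaches no other text. This is a separate drafting gap.

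**What to change.** In Protocol 12.1.3.3, change the Grade 3 figure to >2.0xULN so that it matches SAP Table 8. This is one number, with no new data or procedures, and the running cost is a few more calls to the medical monitor.

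The clinical team should first confirm that 2.5xULN was not a deliberate alert level. If it was, keep the number, remove the Grade 3 label, and tie both the review and the follow-up rule explicitly to 2.5xULN. Grade 3 results in SAP Table 14.3.2.6 could then outnumber the reviews by design, and the report should say so.

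Separately, and as a minor wording alignment, the clinical team should state one ciprofloxacin rule for previously vaccinated Cohort A subjects in footnote d (Protocol Table 1 and SAP Table 2), the synopsis, 8.1, 11.2.5.1 and 12.1.3.5. Which rule to adopt is a clinical choice that the documents do not settle.
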